4.9.1.5. Interim Analyses

No interim analysis is planned for this study. Primary analyses will be conducted after the End of Treatment period when all patients complete Week 25 visit, stay in the study for at least 166 days since the Study Day 1 or withdraw from the study before Week 25 visit. Study results with continuing collected post-treatment data will be updated at the End of Study.

4.9.1.6. Examination of Subgroups

To evaluate the consistency of analysis results in the primary endpoint over parameters such as demographic and baseline characteristics, summaries by subgroup will be provided. Exploratory

TP-GDO-WW-016-08 CONFIDENTIAL Project Document Version No. 2.0
Effective Date: 26 Nov 19 Project Document Effective Date: 13 Dec 2023
Related to: SOP-GDO-WW-019 Page 27 of 61

subgroup analyses may be performed if supported by data. More details are described in the Section 4.9.2.6. The subgroups include the following:

- Age Category (12 to 17, 18 to 39, 40-64, ≥ 65)
- Sex (Male, Female)
- Race (Caucasian, Other),
- Regions (North America, Europe, Middle East)
- Taken any predefined prophylactic therapy, including lanadelumab, berotralstat, C1-esterase inhibitor? (Yes, No)

4.9.2. Primary Efficacy Variable

The primary endpoint is the time-normalized number of Investigator-confirmed HAE attacks (per every-4-week) from Week 1 to Week 25.

Hereditary Angioedema Attack (HAE Attack)

During the study, patients will be instructed to report details of any HAE attack to the study site within 72 hours of the onset of the attack. Throughout the Screening, Treatment, and Post-Treatment Periods, site personnel will contact the patient approximately weekly in order to inquire about any attack that may have occurred.

The presence of these symptoms, including symptoms in one or more predefined locations in the protocol will not automatically be considered an HAE attack unless such a diagnosis is confirmed by the Investigator.

An Investigator-confirmed HAE attack will be defined as an event with signs or symptoms consistent with an attack in at least 1 of the locations noted above. A discrete attack will be counted if there is at least 24-hour symptom-free period between attacks.

Unique Investigator-confirmed HAE Attacks

To be counted as a unique Investigator-confirmed attack distinct from the previous attack, there must be at least 24 hours between the stop date/ time of the first event and the start date/time of the next event, for the attacks to be considered distinct. If there is less than 24 hours between the stop date/time of the first event and the start date/time of the next event, the events will be combined and counted as one unique attack.

When 2 or more events are combined as one unique Investigator-confirmed attack for efficacy analysis, parameters of the derived unique attack with combined multiple events will be defined in a conservative way.

- Events: Investigator-confirmed attacks.
- Dates: The start date/time will be the earliest start date/time of those multiple events; and the end date/time will be the latest end date/time of those multiple events.
- The severity will be defined as the highest severity among those multiple events.

TP-GDO-WW-016-08 CONFIDENTIAL Project Document Version No. 2.0 Effective Date: 26 Nov 19 Project Document Effective Date: 13 Dec 2023 Related to: SOP-GDO-WW-019 Page 28 of 61

- The primary location will be determined by the primary location of individual event, and by following the hierarchy of laryngeal attack, peripheral attack, and abdominal attack. One primary location will be taken; and all the other primary location(s) and secondary locations will be considered as secondary location for the combined attack.
- Regarding the concomitant (allowed or not allowed) medications for the derived unique Investigator-confirmed HAE attack, all records from individual events will be included.

4.9.2.1. Primary Analysis

The primary efficacy endpoint will be tested by the following hypothesis:

```
H_0: \lambda_{ISIS 721744} / \lambda_{placebo} = 1 versus H_1: \lambda_{ISIS 721744} / \lambda_{placebo} \neq 1
```

 $\lambda_{ISIS\ 721744}$ refers to the Investigator-confirmed HAE attack rate from Week 1 to Week 25 in the ISIS 721744 80 mg every 4 weeks group and $\lambda_{placebo}$ refers to the Investigator-confirmed HAE attack rate during the treatment period in the placebo group. The null hypothesis is that the Investigator-confirmed HAE attack rate ratio from Week 1 to Week 25 is 1 (no difference between treatment groups), versus the alternative hypothesis that the Investigator-confirmed HAE attack rate ratio is not 1. Estimated attack rate ratios less than 1 would indicate that patients treated with ISIS 721744 80 mg every 4 weeks, on average, have a lower incidence of Investigator-confirmed HAE attacks from Week 1 to Week 25. The hypothesis will be tested using a Poisson regression model.

The primary analysis will be performed using a Poisson regression model and Pearson chi-square scaling of standard errors to account for potential overdispersion on the FAS. The model will include fixed effect for treatment group (categorical), baseline (the time-normalized run-in period attack rate, continuous), and the treatment-by-baseline interaction as covariates, and the logarithm of time in every-4-week that each patient was observed from Week 1 to Week 25 will be used as an offset variable.

All patients who discontinued the Treatment Period early and started OLE, and patients who discontinued the Treatment Period early and were lost to follow-up before Week 25, will have the time-adjusted attack rate included in the analysis.

The primary analysis will be performed based on the treatment policy strategy. Treatment effect will be estimated regardless of intercurrent events, which are defined in the Section 3.2.1.

From this model, the least squares mean rate, the standard error and the corresponding 95% confidence interval for each treatment group as well as, the model adjusted mean rate ratios of ISIS721744 80 mg every 4 weeks relative to the pooled placebo group and the corresponding 95% confidence interval will be estimated. These estimates will be reported as mean event rates per every-4-week by transforming the estimates using the exponential function. The p-value of the Wald-based chi-square test will be reported for testing the hypothesis.

The percentage difference in mean Investigator-confirmed HAE attack rate between ISIS 721744 80 mg every 4 weeks and the pooled placebo will be calculated as $100\% \times (\text{model adjusted mean rate ratio} -1)$. Similarly, the estimated upper and lower confidence limits for the model adjusted

TP-GDO-WW-016-08 CONFIDENTIAL Project Document Version No. 2.0
Effective Date: 26 Nov 19 Project Document Effective Date: 13 Dec 2023
Related to: SOP-GDO-WW-019 Page 29 of 61

mean rate ratio can be transformed by subtracting 1 and multiplying by 100% to calculate 95% confidence intervals for the percentage change.

In the case when the Poisson regression model cannot be converged, e.g., when all patients within one treatment group have 0 post-baseline Investigator-confirmed HAE event, Fisher's Exact Test will be used for the analysis instead of Poisson regression. The odds ratio, corresponding 95% CI, and p-value will be provided. Sensitivity analyses on FAS described below for the primary endpoint analysis may not be performed.

The comparison between ISIS 721744 80 mg every-8-weeks group and the pooled-placebo group in the time-normalized number of Investigator-confirmed HAE attacks (per every-4-week) from Week 1 to Week 25 will be analyzed in the same way including sensitivity analyses and supportive analyses discussed in sections from 4.9.2.1 to 4.9.2.4

4.9.2.2. Sensitivity Analysis 1 – Negative Binomial (NB) Regression

The Poisson regression model assumes that the mean and variance are equal. When the variance in the data is larger than the mean, the model is said to be over-dispersed. The primary analysis using Pearson chi-square scaling of standard errors to account for potential overdispersion. A sensitivity analysis will be performed by fitting a NB regression (Negative Binomial regression) model, which allows the variance in a different function of the mean. The model will include fixed effects for treatment group (categorical), baseline (the time normalized run-in period attack rate, continuous), and the treatment-by-baseline interaction as covariates, and the logarithm of time in every-4-week that each patient was observed will be used as an offset variable.

All patients who discontinued the Treatment Period early and started OLE, and patients who discontinued the Treatment Period early and were lost to follow-up before Week 25, will have the time-adjusted attack rate included in the analysis.

Strategy used for the primary analysis, the treatment policy, will be used for this sensitivity analysis. Treatment effect will be estimated regardless of intercurrent events, which are defined in the Section 3.2.1.

4.9.2.3. **Supportive Analysis – Per-Protocol Set (PPS)**

Primary analysis and sensitivity analysis 1 described above will be repeated on the PPS. In the case when Poisson regression cannot be converged, e.g., when all patients within one treatment group have 0 post-baseline Investigator-confirmed HAE event, Fisher's Exact Test will be used for the analysis instead of Poisson regression. The odds ratio, corresponding 95% CI, and pvalue will be provided.

4.9.2.4. Sensitivity Analysis 3 – Multiple Imputation Incorporating Pattern Mixture Model

For patients who discontinued the Treatment Period early and started OLE, and patients who discontinued the Treatment Period early and lost to follow-up before Week 25, the primary analysis assumes that the missing data is MAR. To evaluate the robustness of inferences made on MAR, a sensitivity analysis on FAS will be performed based on imputed data by using MI

TP-GDO-WW-016-08 **Project Document Version No. 2.0** CONFIDENTIAL Effective Date: 26 Nov 19 **Project Document Effective Date:** 13 Dec 2023 Related to: SOP-GDO-WW-019

Page 30 of 61

method assuming J2R which is described in Section 4.9.1.3. For each imputed data set, the Poisson regression model used for the primary analysis will be performed. Results will be combined using Rubin's rules.

4.9.2.5. Sensitivity Analysis 4 – Tipping-Point Analysis

A tipping-point analysis will be conducted to measure the potential effect of missing data on the reliability of the primary efficacy analysis.

In this analysis, a range of progressively more conservative assumptions about the number of events occurring in the post-withdrawal period will be explored in order to find the assumption which will reverse the conclusion (i.e., yield a non-significant p-value) of the primary analysis. The assumption that will reverse the conclusion is referred to as the tipping point. Once the tipping point is identified, the clinical plausibility of the assumption can be assessed.

Missing event rate will be imputed by using the MI method described in Section 4.9.1.3. In each run, the Poisson regression model used for the primary analysis will be performed. Results will be combined using Rubin's rules.

The range of assumptions will be determined after treatment unblinding to ensure an appropriate range is explored based on the magnitude of treatment effect and pattern of missing data.

4.9.2.6. Supplementary Analyses of Primary Endpoints

4.9.2.6.1. Subgroup Analyses

Investigator-confirmed HAE attacks (per every-4-week) from Week 1 to Week 25 will be summarized by each subgroup defined in the Section 4.9.1.6.

Typical Patients Subgroup Analyses

During the study conduction, patients that have a clinical history and/or screening period which is atypical for patients with Type I/II HAE may be found that could compromise the interpretation of the efficacy. The list of atypical patients will be determined prior to unblinding for statistical analyses.

Subgroup analyses based on typical patients, i.e., excluding atypical patients mentioned above, will be performed for the following endpoints by using the same methods as described for the primary efficacy endpoint in Sections 4.9.2.1.

- Time-normalized number of Investigator-confirmed HAE attacks (per every-4-week) from Week 1 to Week 25
- Time-normalized number of Investigator-confirmed HAE attacks (per every-4-week) from Week 5 to Week 25
- Time-normalized number of moderate or severe Investigator-confirmed HAE attacks (per every-4-week) from Week 5 to Week 25
- Time-normalized number of Investigator-confirmed HAE attacks requiring acute therapy (per every-4-week) from Week 5 to Week 25

TP-GDO-WW-016-08 CONFIDENTIAL Project Document Version No. 2.0
Effective Date: 26 Nov 19 Project Document Effective Date: 13 Dec 2023
Related to: SOP-GDO-WW-019 Page 31 of 61

4.9.2.6.2. Descriptive Summaries

Investigator-confirmed HAE attack rates as well as change and percent change from baseline in the run-in period will be summarized by treatment group.

The Investigator-confirmed HAE attack rate will be calculated for each patient as the following:

Rate from Week 1 to Week 25: the number of Investigator-confirmed HAE attacks occurring during from Week 1 to Week 25 divided by number of days the patient contributed to the period multiplied by 28 days.

Rate every 4 weeks: Investigator-confirmed HAE attacks will be grouped into 28-day intervals using the start date/time of the Investigator-confirmed HAE attack. First dose date/time will be used as the start of the first interval and end of the interval will be First dose date/time + 28 days. Each successive interval will start from the end of the prior interval, exclusively, and end 28 days later. The Investigator-confirmed HAE attack rate will be calculated for each patient as the number of Investigator-confirmed HAE attacks occurring during each 28-day intervals.

Rate standardized to every-4-week per each week: First, as described above, Investigator-confirmed HAE attack rate will be derived for every 7 days. It then standardized to every-4-week rate by multiply by 4.

4.9.3. Secondary Efficacy Variables

Strategy used for the primary analysis, the treatment policy, will be used for each second efficacy endpoint analysis. Treatment effect will be estimated regardless of intercurrent events, which are defined in the Section 3.2.1.

For secondary endpoints which are count data, i.e., number of HAE related data, in the case when Poisson regression models cannot be converged, e.g., when all patients within one treatment group have 0 event, Fisher's Exact Test will be used as the main analysis. Sensitivity analyses on FAS described below may not be performed.

For secondary endpoints which are responder data, e.g., number of patients with a clinical response on HAE or AECT or with HAE attack-free, in the case when logistic regression models cannot be converged, e.g., when all patients within one treatment group are responders, Fisher's Exact Test will be used as the main analysis. Sensitivity analyses on FAS described below may not be performed.

In the case of convergence problems with the repeated measures mixed model, Section 4.9.3.7 provides alternative model options.

4.9.3.1. Time-Normalized Number of Investigator-Confirmed Hereditary Angioedema (HAE) Attacks (per Every-4-week) from Week 5 to Week 25

The time-normalized number of Investigator-confirmed HAE attacks (per every-4-week) from Week 5 to Week 25 will be analyzed using the same methods as described for the primary efficacy endpoint in sections from 4.9.2.1 to 4.9.2.4.

Main analysis will be based on Poisson regression model on FAS with the treatment policy strategy. For patients who discontinued the Treatment Period early and started OLE, and

TP-GDO-WW-016-08 CONFIDENTIAL Project Document Version No. 2.0
Effective Date: 26 Nov 19 Project Document Effective Date: 13 Dec 2023
Related to: SOP-GDO-WW-019 Page 32 of 61

patients who discontinued the Treatment Period early and were lost to follow-up before Week 25 but after Week 5, will have the time-adjusted attack rate included in the analysis. For patients who were lost to follow-up before Week 5, assuming there is no change on the Investigatorconfirmed HAE attack rate, the baseline Investigator-confirmed HAE attack rate in run-in period will be used.

Sensitivity Analyses

A NB regression on FAS will be performed as a sensitivity analysis.

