ISIS 721744 resulted in a dose-dependent reduction of PKK concentration and plasma proenzyme activation. The difference in absolute and percent change from Baseline for ISIS 721744 vs. placebo was statistically significant for PKK concentration for 40, 60, and 80 mg ($p \le 0.043$) starting at Day 15, the first evaluation, and for 20 mg starting at Day 29, and for plasma proenzyme activation for all doses ($p \le 0.002$) starting at Day 15. The nadir was generally reached around Day 71, when the percent reduction with the 80 mg dose was -93.2% for PKK concentration and -99.6% for plasma proenzyme activation. The difference in absolute and percent change from Baseline in cHK for ISIS 721744 vs. placebo was not statistically significant at any visit.

Phase 2: ISIS 721744 was evaluated in a double-blind placebo-controlled trial in patient with HAE Type I and II in Part A and in an open-label treated patients with HAE-nC1-INH (or Type III). Clinical data demonstrated a significant degree of efficacy of ISIS 721744 80 mg administered once every-4-weeks for 4 months in reducing the rate of HAE attacks in Type I and Type II HAE patients with recurrent attacks over a 16-week (Week 1-17) period vs. placebo (90% reduction in number of HAE attacks compared to placebo; p < 0.001). The percentage of patients who were HAE attack-free from Week 5 to Week 17 was 92.3% as compared to none of the patients treated with placebo. There was also a significant reduction, 95%, in patient treated with ISIS 721744 in the need for use of acute therapies to treat HAE attacks vs. placebo treated patients. Additionally, the number of moderate to severe attack was also markedly reduced with a 96% reduction in ISIS 721744 treated group vs. placebo. There was also a statistically significant reduction in plasma PKK, plasma proenzyme activation and cHK.

ISIS 721744 was well-tolerated with most AEs being mild in severity, and similar in frequency between active and placebo treated patients. The most common TEAE was headache. All the TEAEs had resolved by the end of the study. No LCRIS or flu-like reactions were reported. No deaths or SAEs were reported. There were no clinically relevant changes in the safety laboratories, such as chemistry, hematology, coagulation, complement, inflammatory markers, urinalysis, ECG, or vital sign.

Overall, ISIS 721744 was efficacious and well-tolerated in these patients with HAE.

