10.6.3.2. Secondary Efficacy Analysis

The secondary endpoints include the time-normalized number of Investigator-confirmed HAE attacks (per month) from Week 5 to Week 25; the percentage of Investigator-confirmed HAE attack-free patients from Week 5 to Week 25; the time-normalized number of moderate or severe Investigator-confirmed HAE attacks (per month) from Week 1 to Week 25; the number of patients with a clinical response defined as $a \ge 50\%$, $\ge 70\%$, or $\ge 90\%$ reduction from Baseline (i.e., screening rate) in Investigator-confirmed HAE attack rate between Week 5 to Week 25

compared to placebo; the number of Investigator-confirmed HAE attacks requiring acute therapy from Week 5 to Week 25; percent of patients who are well controlled on the AECT at Week 25; and change in AE-QoL questionnaire total score at Week 25.

The time-normalized number of Investigator-confirmed HAE attacks (per month) from Week 5 to Week 25, the time normalized number of moderate or severe Investigator-confirmed HAE attacks (per month) from Week 5 to Week 25, and the time-normalized number of moderate or severe Investigator-confirmed HAE attacks (per month) from Week 5 to Week 25 will be analyzed in a similar way to the primary efficacy endpoint.

Continuous variables will be summarized by descriptive statistics (n, mean, median, standard deviation, minimum, and maximum) by treatment group. Continuous variables will also be analyzed using a mixed effects model with repeated measures (MMRM). The least-squares means, standard errors, and the 2-tailed 95% confidence intervals for the treatment group and placebo group will be presented.

Categorical variables will be summarized by frequency and percentage for the treatment group and placebo group. Categorical variables will be analyzed using the Chi-squared test or Fisher's Exact test.

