4.9.1.4. Multiple Comparisons/Multiplicity

The multiplicity will be controlled by using a hierarchical ranking strategy in the following testing sequence. Should the null hypothesis for the primary efficacy endpoint be rejected, other endpoints will be tested in order. If any test is not statistically significant, the test(s) at the lower rank will be considered exploratory. Other statistical analyses planed in this SAP but not listed below are considered as exploratory analyses. No adjustment will be made. All tests will be conducted at a two-sided alpha level of 0.05.

- 1. Primary efficacy endpoint analysis: Comparison of the time-normalized number of Investigator-confirmed HAE attacks (per every-4-week) from Week 1 to Week 25 between ISIS 721744 80 mg every 4 weeks group and pooled placebo group
- 2. Comparison of the time-normalized number of Investigator-confirmed HAE attacks (per every-4-week) from Week 5 to Week 25 between ISIS 721744 80 mg every-4-weeks group and pooled-placebo group
- 3. Comparison of the number of patients with a ≥ 70% reduction from baseline in Investigator-confirmed HAE attacks (per every-4-week) from Week 5 and Week 25 between ISIS 721744 80 mg every-4-weeks group and pooled-placebo group
- 4. Comparison of the percentage of Investigator-confirmed HAE attack-free patients from Week 5 to Week 25 between ISIS 721744 80 mg every-4-weeks group and pooled-placebo group
- 5. Comparison of the time-normalized number of moderate or severe Investigator-confirmed HAE attacks (per every-4-week) from Week 5 to Week 25 between ISIS 721744 80 mg every-4-weeks group and pooled-placebo group
- 6. Comparison of the number of Investigator-confirmed HAE attacks requiring acute therapy (per every-4-week) from Week 5 to Week 25 between ISIS 721744 80 mg every-4-weeks group and pooled-placebo group
- 7. Comparison of the change in AE-QoL total score at Week 25 between ISIS 721744 80 mg every-4-weeks group and pooled-placebo group
- 8. Comparison of the time-normalized number of Investigator-confirmed HAE attacks (per every-4-week) from Week 1 to Week 25 between ISIS 721744 80 mg every-8-weeks group and pooled-placebo group
- 9. Comparison of the time-normalized number of Investigator-confirmed HAE attacks (per every-4-week) from Week 5 to Week 25 between ISIS 721744 80 mg every-8-weeks group and pooled-placebo group

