For each of the clinical response, the odds ratio, corresponding 95% confidence intervals and p-value will be provided by using a logistic regression model with the baseline, and the treatment-by-baseline interaction as covariates. Odds Ratio is showing the strength of the association between the treatment effect and the clinical response.

Odds Ratio =
$$(p_1/(1-p_1)) / (p_2/(1-p_2))$$

Where

p₁ = proportion of responder of ISIS 721744 80 mg every 4 weeks (or every 8 weeks)

 p_2 = proportion of responder of the pooled Placebo

Odds Ratio ranges from 0 to infinity. When Odds Ratio = 1, there is no association; when Odds Ratio > 1, patients in the active treatment group are more likely than patients in the placebo group to be responders.

The responder is derived based on time-adjusted Investigator-confirmed HAE attack rate per every-4-week. For patients who discontinued the Treatment Period early and started OLE, and patients who discontinued the Treatment Period early and were lost to follow-up before Week 25, the HAE attack rate per every-4-week for each treatment group is considered as the same before and after withdrawal.

Main analysis will be based on FAS.

Sensitivity Analysis

To evaluate the robustness of inferences made on the main analysis, a sensitivity analysis on FAS will be performed based on imputed data by using MI methods assuming J2R which is described in Section 4.9.1.3. For each imputed data set, the percentage reduction will be calculated and main analysis described above will be performed. Results will be combined using Rubin's rules.

4.9.3.4. Percentage of Investigator-Confirmed Hereditary Angioedema (HAE) Attack-Free Patients from Week 5 to Week 25

The clinical response of Investigator-confirmed HAE attack-free from Week 5 to Week 25 will be analyzed using the same method as described for clinical responses in Section 4.9.3.3.

For patients who discontinued the Treatment Period early and started OLE, and patients who discontinued the Treatment Period early and were lost to follow-up before Week 25, the HAE attack rate per every-4-week for each treatment group is considered as the same before and after withdrawal.

Main analysis will be based on FAS and PPS.

TP-GDO-WW-016-08 Effective Date: 26 Nov 19 Related to: SOP-GDO-WW-019 CONFIDENTIAL Project Document Version No. 2.0

Project Document Effective Date: 13 Dec 2023 Page 34 of 61

Sensitivity Analysis

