5 questions regarding the swelling episodes will be summed up for AAS score calculation. A score between 0 and 3 points is assigned to every question as None = 0 and increase the point from 1 to 3 per severity for each question. The question scores are summed up to an AAS daily score. The daily AAS is summed up to AAS7 and AAS28. Calculation is described as the following: taking the first dose date/time as the start point, sum of daily AAS score during each period divided by the number of days contributed to that period multiplied by 7 days as AAS7 or multiplied by 28 days as AAS28. The minimum number of days for a valid AAS7 and AAS28 is 4 days per week and 3 weeks per 28 days, respectively. Accordingly, the minimum and maximum possible AAS scores are 0–15 for AAS daily score, 0–105 for AAS7, and 0–420 for AAS28.

AAS28 will be compared between ISIS 721744 80 mg every 4 weeks (or every 8 weeks) and pooled placebo using the MMRM model based on the FAS. The MMRM model will include effects of treatment, time, treatment-by-time interaction, and baseline value. The unstructured covariance model will be used to model the within patient errors, shared across treatment and small sample adjustments to standard errors and tests will be made following the Kenward-Roger approach (Kenward and Roger 1997).

AAS scores will be listed in by-patient listings.

4.14. **Other Analyses**

Psychometric analyses will be conducted for selected PRO assessments. Details will be specified in a separate analysis plan.

4.15. **Determination of Sample Size**

The power and sample size estimations were calculated using simulations based on a generalized linear model for count data assuming a Poisson distribution. The primary endpoint is the time-normalized number of Investigator-confirmed HAE attacks (per every-4-week) from Week 1 to Week 25. Assuming an HAE attack rate of 13.26 attacks per 6-month period in the placebo group and an HAE attack rate of 1.38 attacks per 6-month period in the ISIS 721744 80 mg every 4 weeks group, the sample size of 54 patients (2:1 ratio [ISIS 721744 : placebo]) will provide at least 90% power for the primary endpoint, with a 0.05 significance level. A total of approximately 84 patients (42 in the ISIS 721744 every-4-weeks group, 21 in the pooled placebo group, and 21 in the ISIS 721744 every-8-weeks group) will be enrolled in this trial to account for potential early dropouts and to facilitate some general safety evaluations.

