4.16. Changes in the Conduct of the Study or Planned Analysis

The FAS represents the practically feasible intent-to-treat (ITT) population as delineated in International Conference on Harmonization (ICH) Guideline E9. This SAP choose to use FAS for the primary analysis of efficacy.

Responder analyses will be performed by using logistic regression with baseline and the interaction of baseline and treatment groups as covariates, if specified in the SAP. Compare to the Chi-square requested in the protocol, adjustment for baseline related covariates will generally reduce the variability of estimation of treatment effects and thus lead to more powerful hypothesis testing.

Rather than checking the distribution difference between treatment groups as ordinal variables by using a proportional odds model, PGIC and PGIS will be dichotomized to "better" and "no change or worse" and be analyzed for treatment effect by using logistic regression model. Additionally, the change from baseline on PGIS at each visit will be checked for the mean difference as continuous variable by using Wilcoxon Rank Sum test.

TP-GDO-WW-016-08 **Project Document Version No. 2.0** CONFIDENTIAL Effective Date: 26 Nov 19 **Project Document Effective Date:** 13 Dec 2023 Related to: SOP-GDO-WW-019

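### Attack-free status (ranks 4 and 11): with one or two attack-free placebo patients, the SAP's logistic model with treatment-by-baseline interaction is likely to be weaker than the 2x2 test it replaces

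*Combined protocol and SAP*

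**What the plan says.** Protocol 10.6.3.2 sets the test for categorical secondary endpoints: "Categorical variables will be analyzed using the Chi-squared test or Fisher's Exact test".

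SAP 4.9.3.3 replaces this for clinical response with logistic regression on treatment, run-in attack rate and their interaction. SAP 4.9.3.4 extends it: "The clinical response of Investigator-confirmed HAE attack-free from Week 5 to Week 25 will be analyzed using the same method". SAP 4.9.3 returns to Fisher's exact test only "in the case when logistic regression models cannot be converged, e.g., when all patients within one treatment group are responders". SAP 4.16 gives the reason for the change: "adjustment for baseline related covariates will generally reduce the variability of estimation of treatment effects and thus lead to more powerful hypothesis testing".

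In SAP 4.9.1.4, attack-free status is rank 4 for the every-4-week group and rank 11 for the every-8-week group. "All tests will be conducted at a two-sided alpha level of 0.05", and "If any test is not statistically significant, the test(s) at the lower rank will be considered exploratory".

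For the logistic model the SAP does not say whether the p-value is Wald or likelihood-ratio, or at which baseline rate the odds ratio is tested. Appendix A has no logistic sample code.

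**The concern.** With treatment, one covariate and their interaction, the model amounts to a separate logistic regression in each arm. The placebo regression then has two parameters, and few placebo patients are expected to be attack-free. With none, the fit is separated and the rule leads to Fisher. With one or two, the fit usually converges, so the fallback does not apply, although the placebo slope is barely estimable.

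Rank 4 is a gatekeeper. If it misses 0.05, ranks 5 to 24 become exploratory, and these include every confirmatory every-8-week comparison. A miss at rank 11 does the same to ranks 12 to 24. A test chosen because it should be more powerful could lose the hierarchy in data where a 2x2 test is clearly significant.

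**Working it through.** **Inputs from the documents.** Two-sided 0.05 in fixed sequence (SAP 4.9.1.4). Planned arms (SAP 4.15): "42 in the ISIS 721744 every-4-weeks group, 21 in the pooled placebo group, and 21 in the ISIS 721744 every-8-weeks group". Design rates of 13.26 (placebo) and 1.38 (every 4 weeks) attacks per 6 months.

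**Assumptions.** Attack-free proportions; run-in rate of 1 plus a lognormal term (median 3 per 4 weeks), also checked with a normal shape; response unrelated to baseline or falling with it; a Wald test; an arm with no responders, or all responders, treated as non-convergence.

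**1. The plan's own figure.** The only stated power is at least 90% for the primary endpoint with 54 patients. Simulation at 36:18 gives about 100%, and 99.8% with variance 10 times the mean, so it holds as a lower bound. No power is stated for attack-free status.

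**2. Chance of one or two attack-free placebo patients.** With 21 patients and true proportion p, this is 21p(1-p)^20 + 210p²(1-p)^19:

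| p | 1% | 2% | 5% | 10% |
|---|---|---|---|---|
| Chance | 19% | 34% | 57% | 54% |

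The design rate gives 13.26 × 20/26 = 10.2 to 13.26 × 20/24 = 11.05 expected placebo attacks over 20 weeks. Plain Poisson then gives P(attack-free) = exp(-10.2) to exp(-11.05), about 0.00004 to 0.00002. A negative binomial, (1 + m/k)^(-k), gives 2-3% for shape k = 2 and 8-9% for k = 1 (shapes assumed).

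**3. Fixed counts: 22/42 against 1/21.** Fisher and chi-square both give p = 0.0002.
- Unadjusted logistic Wald: log odds ratio = ln[(22 × 20)/(20 × 1)] = ln 22 = 3.09; SE = √(1/22 + 1/20 + 1/1 + 1/20) = 1.07; z = 2.89; p = 0.004.
- SAP model: converges in 85-91% of simulated data sets. If response is unrelated to baseline, the sole placebo responder has the highest or lowest run-in rate with probability 2/21, and 1 - 2/21 = 90% agrees with this.
- Tested at the mean baseline: median p 0.012-0.075, significant in 43-70% of converged fits (76-81% with a normal-shaped baseline).
- Tested as the arm coefficient, that is at a baseline of zero: median p 0.35-0.40, significant in 6-22% (1-4% with the normal shape).
- Same data without the interaction: Wald median p 0.003-0.004, significant in 100%.

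For 22/42 against 2/21, Fisher p = 0.0009 and the SAP model at the mean baseline is significant in 49-88%. For 10/21 against 1/21 (rank 11), the figures are 0.0036 and 26-64%.

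**4. Power at 0.05.** Ranges run over the baseline-response assumption.

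| Comparison | Attack-free, active / placebo | Fisher | Chi-square | SAP rule, mean baseline | SAP rule, baseline 0 |
|---|---|---|---|---|---|
| Rank 4, 42 vs 21 | 35% / 5% | 0.81 | 0.83-0.84 | 0.46-0.58 | 0.40-0.44 |
| Rank 4 | 45% / 5% | 0.95-0.96 | 0.97 | 0.60-0.79 | 0.43-0.48 |
| Rank 4 | 45% / 10% | 0.82-0.83 | 0.85 | 0.40-0.65 | 0.20-0.26 |
| Rank 11, 21 vs 21 | 45% / 5% | 0.84-0.85 | 0.91-0.92 | 0.56-0.70 | 0.42-0.45 |

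At 38% against 1%, a further run gives Fisher 98-99% and the SAP rule 88-89%. With a placebo proportion of 0.0001 both give 0.99.

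**5. Which element causes the loss.** A separate simulation (42 vs 21, rate ratio 0.19, gamma patient rates with added frailty) kept the fallback trigger and removed only the interaction:

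| Placebo attack-free | Fisher | SAP model | Without interaction |
|---|---|---|---|
| 7% | 82% | 53% | 81% |
| 10% | 69% | 44% | 69% |
| 16% | 57% | 41% | 59% |

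Removing the interaction recovers essentially all of the loss.

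**The case against.** The strongest reply is that the damaging case may not arise. Protocol 2.3.4 reports for Phase 2: "The percentage of patients who were HAE attack-free from Week 5 to Week 17 was 92.3% as compared to none of the patients" on placebo. With zero, the SAP reaches Fisher and loses nothing, and under plain Poisson at the design rate one attack-free placebo patient would be remarkable. This stands as a limit: the loss is conditional on one or two such patients. But the Phase 2 window was shorter (Week 5 to Week 17), and the SAP itself plans for overdispersion, which makes small non-zero counts plausible.

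Several stronger readings are tempting, and the documents do not support them:
- **That the logistic p-value is close to worthless.** This fits only a test of the arm coefficient at a baseline of zero, a rate no eligible patient is likely to have, since two attacks in 56 days is 2/56 × 28 = 1 per 4 weeks. The SAP's Poisson sample code compares least-squares means, which points to the mean baseline. There the test is weakened but often still significant.
- **That logistic regression or the convergence trigger is the defect.** Steps 3 and 5 of the working show otherwise.
- **That the protocol specified Fisher.** It allows chi-squared or Fisher; either leads to the same conclusion.
- **That SAP 4.16 is simply wrong.** It says adjustment generally helps. The rationale fails for this model on this endpoint.
- **That the hierarchy did fail at rank 4.** The documents give no attack-free counts, and the plain-language summary calls the every-8-week reduction significant.

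It also stands that Wald is an assumption here: the SAP names it only for the primary Poisson model. A likelihood-ratio test at the mean baseline was significant in 100% of the 22/42 against 1/21 data sets, but a likelihood-ratio version showed 7-8% type I error in simulation. No type I error inflation is shown for the SAP rule, so the risk is to the sponsor's own claims.

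**Conclusion.** The concern holds in a conditional form, as a should-fix. If one or two placebo patients are attack-free, the planned analysis usually converges and is materially weaker than the protocol's test. Assuming a Wald test at the mean baseline, overall rank 4 power falls by roughly 10 to 30 points or more below Fisher's, with a similar pattern at rank 11 (0.56-0.70 against 0.84-0.85 at 45% vs 5%). The loss is larger if the test is made at a baseline of zero, and absent if no placebo patient is attack-free. The cause is a placebo slope estimated from one or two responders and then tested by Wald. For this endpoint that contradicts the power rationale in SAP 4.16. The direction held under every baseline assumption tried in which such counts occur with appreciable probability; the size depends on attack-free proportions and a run-in distribution that the documents do not give.

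**What to change.** In SAP 4.9.3.4, make Fisher's exact test, which protocol 10.6.3.2 allows, the main test for ranks 4 and 11 with no convergence condition. Keep the logistic model as supportive, either without the interaction or with the odds ratio reported at a stated baseline rate. Alternatively, drop the interaction from the main attack-free model and keep the present fallback. In either case name the logistic test statistic, and limit the statement in SAP 4.16 so that it no longer claims a power gain for this endpoint.

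The cost is SAP wording. With Fisher the main test loses baseline adjustment; its null rejection rate in simulation was about 4% or lower. There is precedent within the SAP: 4.9.3.6 already omits baseline and interaction from the main AECT responder test. No new count-based trigger is needed for the other responder ranks. The choice should be fixed before unblinding; after database lock, SAP section 1 requires it to be documented as a deviation.
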